An independent group of experts in urology, urogynecology, biostatistics, clinical trials, behavioral medicine, nursing, and ethics who are not otherwise involved in the study has been appointed by the NIDDK to review periodically the progress of the study. Such monitoring will include at least the following: review of study protocols prior to implementation; monitoring of patient accrual; review of reported adverse events; monitoring of protocol compliance; review of data analysis plans; monitoring data quality, and interim monitoring of study endpoints.

PROTOCOL

A. STUDY AIMS

The primary aim of this randomized clinical trial is to compare the Burch modified Tanagho and autologous fascia sling procedures for overall treatment success and stress-related symptoms at a minimum of 24-months post-surgery in women with predominant stress incontinence.

The secondary aims of the trial are:

- to compare complications including voiding dysfunction, quality of life, sexual function, satisfaction with treatment outcome, and need for additional surgery or other postoperative treatment for the two surgical procedures;
- to determine the prognostic value of urodynamic studies and to identify urodynamic parameters that predict treatment success in each surgical procedure.

B. BACKGROUND AND SIGNIFICANCE

B.1 Urinary Incontinence: Prevalence and Impact

Of the estimated 16 million Americans who suffer from urinary incontinence (Fantl, Newman, Colling, & al, 1996), two-thirds are women. Individuals with incontinence suffer social isolation, sexual and relationship dysfunction, and depression (Hunskar & Vinsnes, 1991). The monetary cost to society is over \$26 billion annually; most of this money is spent on the consequences of incontinence, not on its treatment (Wagner & Hu, 1998). Urinary incontinence remains an under-reported and under-treated condition. Patients suffer in silence because they think incontinence is a normal part of aging, or they feel embarrassed to discuss the problem with their physician (Norton, MacDonald, Stanton, & Sedgwick, 1988). In spite of these staggering statistics, there have been surprisingly few rigorously conducted scientific studies on the epidemiology, etiology or treatment of incontinence. The field suffers from a general lack of uniformity and standardization in the incontinence literature.

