Comparisons and contrasts between the Burch colposuspension and the pubovaginal sling are more subtle. First, the success rates reported for the pubovaginal sling are similar to those reported for the Burch, with one important difference: the sling has traditionally been reserved for patients undergoing secondary procedures. It has been argued that higher success rates for the sling might be seen if the sling would be promoted for use in primary cases. The WHO-sponsored International Consultation on Incontinence (Jarvis et al., 1999) compared the three randomized trials and one prospective trial of the pubovaginal sling and Burch colposuspension procedures, and concluded that the success rates for these procedures were equivalent, although only one of the studies reported the randomized comparison as a primary operation (Lalos, Burglund, & Bjerle, 1993). These prospective studies suffer from small numbers (see Table 1), while the dozen retrospective studies have considerable methodological problems. One study by Iosif (1983) found a higher cure rate for the Burch (95%, 95%CI 91-98%) compared to pubovaginal sling (79%, 95%CI 72-85%).

Table 1: Sling vs. Burch Colposuspension*

	Sling		Burch	
	n	dry n	n	dry n
(Henriksson, 1978)	15	15	15	15
(Lalos et al., 1993)	14	11	22	17
(Enzelsberger, 1996)	36	33	36	31
(Richmond, 1989)	14	9	15	12
		86%		85%

* Summary from the Female Surgical Treatment group from the WHO First International Consultation on Incontinence, Jarvis et al (1999)

It has been suggested that complications, including voiding dysfunction and detrusor instability, are higher with the sling procedure (Ostergard, 1997). Two comparative studies have conflicting conclusions with respect to the complications of these two procedures. In women undergoing secondary procedures, Enzelberger and colleagues (1996) found a 13% incidence of *de novo* voiding dysfunction after sling procedures but not Burch procedures, while Marinkovic and colleagues (1998) found that there were fewer immediate complications associated with the pubovaginal sling compared to the Burch colposuspension (42% Burch versus 26% sling). Although the Burch seems to be a durable procedure after five and even ten years, there are few data on the durability of the pubovaginal sling, especially as a primary procedure.

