*Patient can be deferred for enrollment until respective time interval has been met.

E.2 Exclusion Criteria

1. Age < 21 years
2. Non-ambulatory (Ambulatory with assistive devices does not exclude the patient.)
3. Pregnancy by self-report or positive pregnancy test, or self-reported intention to become pregnant in the next 24-months
4. Current cancer chemotherapy or radiation therapy
5. Systemic disease known to affect bladder function (i.e., Parkinson's disease, multiple sclerosis, spina bifida, spinal cord injury or trauma)
6. Urethral diverticulum, current or previous (i.e. repaired)
7. Prior augmentation cystoplasty or artificial sphincter
8. < 12 months post-partum*[†]

9. Recent pelvic surgery (e.g. vaginal hysterectomy), i.e., endoscopic pelvic surgery <6 weeks or open pelvic surgery <6 months*
10. Participation in another treatment intervention trial that might influence the results of this trial.

*Patient can be deferred for enrollment until respective time interval has been met.

†“Partum” is defined as a delivery or other termination that occurs after 20 weeks.

If more than 6-months transpires between determination of eligibility and surgery, specified measures must be repeated to ensure current eligibility for the trial as well as to obtain current baseline values for critical measures that are subject to change. (See Section H.5 and Appendix A.)

F. RANDOMIZATION

Patients will be randomized in the operating room. It is recognized that there are disadvantages to this strategy, including the following points:

- Patients must agree to be blinded to the type of surgery they will get until after the operation;
- The surgeon(s) must be prepared to perform either type of procedure;
- The anesthesiologist must be willing and able to evaluate the patient without knowing which procedure will be performed.

The process of obtaining the randomized treatment assignment will be accomplished via a telephone call to an automated randomization system at the Biostatistical Coordinating Center (New England Research Institutes) from a touchtone telephone. A back-up hard copy of the assignment kept in a sealed envelope will be made available in the case of technical problems. Randomization will be stratified by clinical site, using permuted blocks.

G. TREATMENTS

G.1 Operative Procedures

The two procedures included in this trial are the Burch modified Tanagho procedure and the autologous fascia sling procedure.

G.2 Standardization of Operative Procedures

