Fisher's exact test will be used for unadjusted analysis of the primary endpoints and other dichotomous outcomes (e.g. complication rates). Time-to-failure analyses (Kaplan-Meier plots and logrank tests) will also be used in secondary analyses of the primary outcome as described above under "Interim Monitoring." Treatment comparisons will be adjusted for covariates with the logistic model for dichotomous endpoints and proportional hazards models for time-to-failure analyses. Analysis of continuous outcomes such as the quality of life subscales will be based on change from baseline. Prognostic models will be developed using baseline urodynamic testing results and other baseline covariates to explore the extent to which baseline measures can be used to predict surgical success. Time-to-event methods will be utilized to characterize time to normal voiding. In addition to comparing treatment groups with respect to satisfaction with surgery, the analysis of this outcome will include an evaluation of expectations of surgery as a predictor of satisfaction.

L. RECRUITMENT

To assess ability of the nine clinical centers to enroll the required number of patients (73 patients per center) into the trial over a two-year period, each center provided data in July 2001 regarding the number of Burch and sling procedures performed over the prior 12-months. These data are displayed in Table 2. Based on these data and the estimated enrollment rate of 20% of eligible patients, there appear to be a sufficient pool of patients from which to recruit. In the event that the enrollment rate has been overestimated (i.e. fewer patients agree to participate in the trial), several additional sources of potential patients have been identified:

- Investigator's office (might include patients of a non-study surgeon in a group practice);
- Referrals from colleagues;
- Post-card announcements in clinical areas/offices;
- Advertising: newspapers; newsletters; cable TV or public service announcements; websites of professional organizations, advocacy groups, or NIH; health fairs, health clubs, billboards;
- Mailings to enriched lists, e.g., former patients.

Table 2. Number of Procedures by Site: Approximate 12 Months prior to July 2001

Site	Burch	Sling
University of Alabama - Birmingham	68	162
University of California - San Diego	123	152
University of Maryland	46	155
University of Pittsburgh	33	297
University of Texas - Dallas	141	102

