Appendix B. Complications of Surgery

A. Serious complications that mandate report to the DSMB within 72 hours:

1. Acute serious morbidity and mortality related to surgery: death; myocardial infarction; cerebrovascular accident; pulmonary embolus; renal failure; sepsis requiring admission to ICU; major anesthetic misadventure requiring admission to ICU.
2. Complications which contribute to serious morbidity on a subacute or chronic basis: abscess or infected hematoma that requires open or percutaneous intervention; injury to adjacent organ (injury to bladder, bowel, ureters, or vascular structures) which requires open, percutaneous, or endoscopic operations; fistula; nerve injury (specify site); deep venous thrombosis.

B. Complications of moderate or minor concern that are reportable to the DSMB at set intervals:

1. Complications which are of moderate concern and contribute to morbidity on a chronic basis: sling erosion; hernia; need for transfusion.
2. Short-term complications or minor complications: wound separation; hematoma, or seroma NOT specified above; atelectasis; pneumonia; cystitis or pyelonephritis (any antibiotics given for urinary tract symptoms); anesthetic minor complication (including aspiration pneumonia, laryngospasm, infection at catheter site); bladder injury.

C. Site-specific complications or deviations:

The DSMB must consider these complications in the light of individual surgeons and sites, including procedure-specific differences in primary outcome (cure of incontinence) and important but less serious complications (need for take-down.) A single surgeon or site that deviates significantly from the rest of the network should be evaluated for proficiency in that procedure, and consideration given to exclusion of data from that surgeon and/or site from final analyses.

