- Emergency room admissions: date, reason for each
- Additional abdominal or pelvic surgery: date, procedure, reason
- Medication Audit
 - Antibiotics: type, # days
 - Pain med: type, # days, # pills
- Resumption of spontaneous voiding
 - If catheter at discharge: date removed, residual urine volume at removal
 - If intermittent catheterization, when stopped
- Urine incontinence: frequency, type
- UTI: dates and treatment
- Persistent pain at site of surgery: duration, description
- Number of lost work days
- Resumption of normal activities

Measures for all Follow-up Points

- Persistent pain at site of surgery (i.e. >6months = “complication”)
- Develop hernia: describe
- Develop vaginal prolapse: describe – POP-Q and self-report
- Develop new UI: describe
- Change in bowel movements: describe
- Develop new fecal incontinence: describe
- Develop new sexual dysfunction: describe

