Appendix D. Guidelines for Post-Operative Instructions

ACTIVITY:

Rest as much as needed during the first two weeks after your procedure.
Avoid heavy lifting, pushing or pulling.
Lifting: Limit your lifting to about 10 lbs for the first 4-6 weeks post-op (About a gallon of milk).
Discuss heavier lifting with your doctor at your post-op visit.
Avoid standing for prolonged periods of time.
Climbing stairs is allowed.
Talk to your doctor about when you may resume usual physical activity.

NUTRITION:

Resume your normal diet.
Drink 6-8 glasses of non-caffeinated beverages daily.
Eat a well-balanced diet.

ELIMINATION:

It is important not to strain during bowel movements.
Narcotics tend to make you constipated.
Preventing constipation is easier than treating it!
Eat a high fiber diet (fruits, vegetables, and bran).
Take a stool softener once or twice daily.

If constipation should occur:

You may take a mild laxative (Milk of Magnesia).
Add fruit and bran to your diet.
Drink more liquids.

Call your doctor or nurse if you experience burning on urination or urgency frequency or you feel that you are unable to completely empty your bladder.

VOIDING:

Avoid bladder distension.
Void every 2-3 hours, whether you feel like you have to or not.
Your sensation of fullness may be altered by anesthetics, swelling or repositioning of a previously prolapsed bladder.
If additional bladder care is required, you will receive instructions from your doctor or nurse.

HYGIENE:

You may shower and wash your hair. If your incisions are closed, you may bathe unless your doctor tells you otherwise. Do not douche or use tampons until after your follow-up appointment.

FEVER:

If you feel feverish or have shaking chills, take your temperature. If your temperature is 100.4°F (38°C) or above, call your doctor. The fever may mean there is an infection.

ABDOMINAL INCISION CARE:

Clean the incision with water. Do not use a dressing unless the incision is draining or irritated. If you have small adhesive strips in place, and they do not fall off within 10 days, carefully peel off. Check your incision daily for redness, draining, swelling or separation of the skin. Call your doctor if you notice any of these.

VAGINAL DISCHARGE:

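### Appendix B records any antibiotic given for urinary symptoms as urinary infection, so the infection rate can partly recount non-infective voiding symptoms and the two cannot be separated afterwards

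*Protocol*

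**What the plan says.** Appendix B, item B.2, places urinary infection among the short-term or minor complications reported to the DSMB at set intervals. The entry reads "cystitis or pyelonephritis (any antibiotics given for urinary tract symptoms"). Section J says that the DSMB approved the list in Appendix B and that it also appears on the Adverse Event Form. The wording therefore governs what sites record.

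Appendix C, in the block that runs through 3 months, adds "UTI: dates and treatment" and an audit of antibiotic type and number of days. Neither entry asks for a culture or urinalysis result.

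One secondary aim in Section A is "to compare complications including voiding dysfunction, quality of life, sexual function" and other outcomes. Section K.3 states: "Fisher's exact test will be used for unadjusted analysis of the primary endpoints and other dichotomous outcomes (e.g. complication rates").

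On arm differences, Section B.3 reports a suggestion that complications, including "voiding dysfunction and detrusor instability, are higher with the sling procedure". It then says that two comparative studies disagree.

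On blinding, Section F says only "Patients must agree to be blinded to the type of surgery they will get until after the operation". The surgeon carries out the assigned procedure, and no blinding of later clinicians is stated.

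**The concern.** The event is set off by a prescription, not by evidence of infection. Urgency and frequency are urinary tract symptoms. They can come from infection, but also from voiding dysfunction or new detrusor instability, which this trial compares between arms in their own right. A woman with non-infective urgency who receives an antibiotic is recorded as having cystitis or pyelonephritis.

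If such symptoms are more frequent in one arm, that arm will also show more infection even when true infection is equal. One harm is then counted twice in the comparison of complications. This matters because Section B.3 cites a decision analysis in which the choice between the procedures turned on retention and new detrusor instability.

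An analysis plan cannot repair this from the listed data. Without a field for confirmation, treated infection and treated symptoms look the same in the database. The item also puts upper-tract infection under the same label as a treated symptom.

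**Working it through.** **The plan's own figure.** The protocol gives no rate for urinary infection. Its sample size is used here only to supply the number per arm. For 60% versus 72%, two-sided alpha 0.05 and 260 per group, the exact power of Fisher's test is 80.0%, as Section K.1 states. Inflation for 20% non-compliance gives 260 / 0.80 = 325 per group, which also agrees.

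**Can confirmed infection be recovered from the listed data?**

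| Source | What is recorded | Separates infection from empirical treatment? |
|---|---|---|
| Appendix B, item B.2 | antibiotic given for urinary symptoms | No |
| Appendix C, through 3 months | dates and treatment of UTI; antibiotic type and days | No |
| Appendix C, through 3 months | complications specified; readmission and emergency-room reasons | May identify some pyelonephritis; does not confirm cystitis |
| Appendix C, all follow-up points | UTI not itemised | No |
| Appendix A | complications ticked at each follow-up contact to 24 months | Same definition applies |

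**Size, under assumptions.** Let t be the true infection rate, equal in both arms; s the rate of non-infective urinary symptoms among the others; and e the share of those given an antibiotic. The recorded rate is

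r = t + (1 − t) × s × e.

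None of t, s or e is in the protocol. Assume t = 20%, s = 10% (Burch) and 20% (sling), and e = 25% to 75%. The last column is the chance that Fisher's exact test gives p ≤ 0.05 at 325 per arm.

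| e | Burch | Sling | False difference | Chance of p ≤ 0.05 |
|---|---|---|---|---|
| 0.25 | 0.20 + 0.80 × 0.10 × 0.25 = 22% | 0.20 + 0.80 × 0.20 × 0.25 = 24% | 2 points | 8% |
| 0.50 | 24% | 28% | 4 points | 19% |
| 0.75 | 26% | 32% | 6 points | 36% |

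With no misclassification and t = 20% in both arms, the chance is 4.0%. With the same s and e, moving t from 15% to 30% leaves the false difference between 0.70 × 0.10 × 0.25 = 1.75 points and 0.85 × 0.10 × 0.75 = 6.4 points. Exchanging the two symptom rates reverses the sign and leaves the size unchanged.

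**Sensitivity to the inputs.** Over a wider assumed grid (t from 5% to 30%; s of 0% vs 13%, 5% vs 13% or 10% vs 20%; e from 25% to 100%, including 25% in Burch against 50% in sling), the chance of a significant result at 325 per arm runs from 5.6% to 99.9%. The assumptions decide the answer, so these figures show that the mechanism can matter and do not predict its size.

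**The case against.** **It is a safety-reporting list, and the item is minor.** A sensitive trigger is defensible for safety reporting, and the parenthesis could be read as the treatment threshold at which a diagnosed infection becomes reportable. UTI is not named in the secondary aim, nor among the complications that Section K.2 singles out for review by site and surgeon. This limits the importance of the point. It does not remove it: the parenthesis is the only criterion given, and Section K.3 applies a between-arm test to complication rates in general. How events are grouped can be left to an analysis plan, but a distinction that was never recorded cannot be restored there.

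**The direction is not established.** This stands. Section B.3 calls the comparative studies conflicting. One reports 13% new voiding dysfunction after sling but not Burch, in women having secondary procedures, and its title in the reference list names a different sling material from the one used here. The other reports fewer immediate complications after sling (26% versus 42%). A reader might infer that the definition will make the sling look worse; the protocol does not support that.

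**Arm-dependent prescribing is conjecture.** This also stands. A reader might infer from the limited blinding that prescribing will differ by arm. The protocol does not say who prescribes or that knowing the procedure would change the decision. The advice in Appendix D, "Call your doctor or nurse if you experience burning on urination or urgency frequency", is an optional guideline common to both arms. The point needs only a difference in symptoms.

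**Pyelonephritis is not wholly hidden, and detail is short-term.** Specified complications and readmission reasons may identify some cases. UTI detail is itemised only through 3 months, although complications are ticked to 24 months. The stronger claims, that upper-tract infection is invisible or that two full years of detailed UTI data are affected, are not supported.

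**Confirmation is discretionary too.** Tests obtained in care are ordered by clinicians who may know the arm, and women with more symptoms may be tested more often. A comparison restricted to confirmed events can therefore also be biased. This objection is sound and shapes the fix.

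**Conclusion.** The point holds as a weakness in how one secondary complication is defined and recorded. Followed as written, Appendix B counts empirically treated urinary symptoms as infection, and the data listed in Appendix C do not allow the two to be separated later. If non-infective symptoms differ between arms, a false difference in infection can arise in either direction.

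Its size is unknown. The illustration of 2 to 6 points rests on equal true infection, an assumed doubling of symptoms in one arm and an assumed share treated; true infection may itself differ between the procedures. Neither primary endpoint uses this item. A stricter definition may exist in the Manual of Operations, which is not at hand; if so, Appendix B should be brought into line with it.

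**What to change.** On the Adverse Event Form and in Appendix B, split the item into three:

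- (a) pyelonephritis;
- (b) cystitis supported by a culture or urinalysis already obtained in care;
- (c) antibiotics given for urinary symptoms without such confirmation.

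Report by arm the number of women with at least one event in each category and in the union, which reproduces the present definition, so nothing is lost. Read (c) beside the urgency and voiding-dysfunction results. Do not label the union as infection or rest a conclusion about infection on it alone, and do not make (a) plus (b) the sole infection comparison.

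The cost is one extra form field. No test is required and no treatment changes. The report should state two limits: (a) plus (b) misses infections treated without a test, and it may differ by arm because testing is discretionary.

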Because the urge component of incontinence in women with mixed incontinence is not expected to be improved by either surgical procedure being studied, the requirement of negative self-report and negative pad test may prevent women from achieving the clinical endpoint of "overall treatment success" even if the surgery is successful in eliminating the stress component of incontinence. Therefore, although many reports of both Burch and sling procedures suggest "success" rates of approximately 80-85%, we expect to observe lower success rates in this trial, by approximately 15-20 percentage points. A sample size of 260 per group, or 520 total, would

ensure 80% power to detect a 12 percentage point difference (60% vs. 72%) using a two-sided $\alpha=.05$ Fisher's exact test. In order to meet the criteria for success, patients must be willing to undergo a fairly intensive measurement process (self-administered questionnaire, 3-day diary, 24-hour pad test, stress test). It seems likely that some women who consider themselves to be cured will not comply with this regimen. Therefore, to adjust for a 20% non-compliance rate, the target sample size will be inflated to 325 per group, or 650 total.

For the more mechanistic endpoint, “treatment success specific to SUI,” we assume a higher success rate, i.e., >80%. The target sample size will ensure >85% power for detecting a 10 percentage point difference (80% vs. 90%).

K.2 Interim Monitoring

Ordinarily, early stopping rules are based on monitoring the primary endpoints for a treatment difference so large that it is unethical to continue treating one group of patients with the “inferior” treatment, and on monitoring the treatments for safety. In this trial, however, several considerations argue against the usual motivations for early stopping procedures.

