First, we expect very little primary endpoint data to be available while any participants are still at risk for exposure to either surgery being evaluated. Accrual is expected to take 24-months and success on the primary endpoints is not documented until 24-months after surgery. Therefore, at the time the first participants are reaching the assessment time for documenting “success”, all or nearly all patients will already have had their surgery. Nevertheless, there will be some information on the primary endpoints prior to 24-months, since self-reported stress-type symptoms, a positive diary, positive pad test or positive stress test at 6-24 months, or retreatment for SUI at any time prior to 24-months will be considered a failure.

Second, both the Burch modified Tanagho and the autologous fascia sling procedures are “standard” surgical procedures. Unlike a trial evaluating a new surgical procedure, the study procedures in this trial have generally well-known complications. It is unlikely that we will experience any new or unexpected complications. Of course, we will collect and document complications but we do not expect that treatment group differences in surgical complication rates would pose an ethical imperative to stop the trial, unless some serious unexpected complication is prevalent. Rates of the more serious surgical complications (e.g. organ damage, sling erosion, hernia, wound infection) will be summarized separately within each site and further within each surgeon, to monitor for problems with specific hospitals or surgeons.

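### Appendix B permits a surgeon's or site's data to be left out of the final analyses after a look at the primary outcome by procedure, which can bias the comparison, can inflate the type I error and costs power

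*Protocol*

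**What the plan says.** Appendix B, part C, directs the DSMB to look at complications by surgeon and site, "including procedure-specific differences in primary outcome (cure of incontinence) and important but less serious complications (need for take-down". It continues: "A single surgeon or site that deviates significantly from the rest of the network should be evaluated for proficiency in that procedure", with "consideration given to exclusion of data from that surgeon and/or site from final analyses". It names no test, significance level, direction, minimum number of women or timing for this decision, and it does not confine the exclusion to a sensitivity analysis.

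Three other places bear on the point:

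- Section F: "Randomization will be stratified by clinical site, using permuted blocks". Surgeon is not a stratification factor.
- Section K.3: "Fisher's exact test will be used for unadjusted analysis of the primary endpoints". The section removes nobody from the analysis, but it contains nothing that overrides Appendix B.
- Section K.2: rates of the more serious surgical complications are to be "summarized separately within each site and further within each surgeon". This is safety monitoring and says nothing about leaving data out.

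**The concern.** Which women stay in the final comparison may be settled after randomisation, by people who have seen how each procedure performed at each site. If a site is dropped because one procedure did badly there, the estimate moves towards that procedure. If the decision depends on results and follows no stated rule, the p-value of the primary test has no known error rate. Section B.4 justifies randomising on the ground that it removes confounding from surgeon preference and from differing patient populations and referral patterns. Selecting surgeons or sites on outcome gives part of that protection away.

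The protocol states this rule; it is not a detail left open for a statistical analysis plan.

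**Working it through.** **Inputs from the protocol.** Success 60% v 72%, two-sided 0.05 Fisher's exact test, 80% power, 260 evaluable per group, 20% non-compliance, 325 per group or 650 in total (K.1). Nine centres, 73 women each (L).

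**Assumptions, because the protocol gives no rule.** A cell is one procedure at one site, and it deviates if a two-sided z test against the other sites passes the threshold. Sites are equal in size. True success is 66% in both arms (the midpoint of 60% and 72%). The final test in the simulations is a pooled z test.

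**1. The plan's own figures.** With mean rate 0.66 and difference 0.12:

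n = [1.96·√(2·0.66·0.34) + 0.842·√(0.60·0.40 + 0.72·0.28)]² / 0.12² = 244 per group.

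The continuity correction brings this to 260, and exact Fisher power at 260 per group is 80.0%. Inflation: 260/0.80 = 325. Per site: 650/9 = 72.2, hence 73. Evaluable women per arm per site: 260/9 = 28.9, taken as 29. The design figures reproduce.

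**2. Chance of a flag with identical sites and no treatment difference.** Nine sites × two procedures = 18 cells. If the cells were independent, P(at least one flag) = 1 − (1 − a)^18.

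| Threshold a | Formula | Simulated | Type I error if all flagged sites are dropped |
|---|---|---|---|
| 0.05 | 60% | 59% | 6.9% |
| 0.01 | 17% | 16% | 5.8% |
| 0.001 | 1.8% | 1.6% | 5.0% |

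With every site kept, the simulated type I error is 4.9%. Repeat runs of the simulation differ by a few tenths of a point.

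**3. Shift in the estimate, homogeneous sites.**

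- Whole sites dropped under a symmetric rule (a deviation in either direction, or low success on either procedure): the mean difference stays near zero.
- Sites dropped only when low in one named arm, threshold 0.05: this happens in 24.5% of trials and moves the difference by about 2.6 points in those trials. Over all trials: 0.245 × 2.6 ≈ 0.6 points. The design difference is 12 points.

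**4. Shift when sites vary more on one procedure.** As an illustration, let sling results vary between sites with a logit SD of 0.5 (assumed) and Burch results not vary. Dropping any site with low success on either procedure then moves the mean sling-minus-Burch estimate from −0.8 to +1.8 points. The rule treats both procedures alike, yet the result is not neutral. Uneven experience is visible in Table 2 of section L: 636 Burch and 65 sling procedures at one site, 5 and 93 at another.

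**5. Power.** One site lost: 260 − 29 = 231 per arm, Fisher power 75.2%. Two lost: 202 per arm, 69.0%.

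Surgeon-level exclusion is not quantified, because the protocol does not give the number of surgeons.

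**The case against.** The clause is softer than it may look. Proficiency evaluation comes first, exclusion is only to be considered, and the body addressed is an independent DSMB. Dropping a whole site removes both arms, and randomisation is stratified by site. Several inferences that a reader might draw therefore go too far:

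- *That the clause does bias the primary comparison.* It permits exclusion and fixes no direction. A symmetric whole-site rule with homogeneous sites leaves the mean difference near zero. Only 'can bias' is supported.
- *That chance will usually produce a site to exclude.* This holds at 0.05 per cell, but that level is an assumption. The only numerical flag for the DSMB in the protocol is the .001 level in K.2, which concerns treatment differences on any endpoint and not sites. At 0.001 per cell the type I error is essentially unaffected.
- *That someone would keep or drop flagged sites according to which p-value is smaller.* All-or-none discretion of that kind at the 0.05 threshold would give about 8.0%, but nothing in the protocol describes such a choice.
- *That the 2.6-point shift applies generally.* It applies only in the trials where a site low in one named arm is dropped.
- *That K.2 carries the same defect.* It covers safety monitoring by site and surgeon, which is proper.

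An analysis plan may also exist that defines the analysis set, so the lack of such a definition in K.3 is no fault in itself.

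What remains after all this is the sentence in Appendix B. Its trigger includes the primary outcome by procedure, its consequence is removal of randomised women from the final analyses, and nothing else in the protocol limits it.

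**Conclusion.** The clause is wrong as written and should be removed. That rests on the text alone: it permits outcome-dependent exclusion from the final analyses under no stated criterion.

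The size is uncertain and probably moderate. Under the assumed cell-by-cell rule, the type I error lies between essentially nominal and about 7%, depending on the threshold. These levels come from a pooled z test; Fisher's exact test is more conservative, so the absolute levels under it would be somewhat lower. Bias in the estimate needs one-directional removal or sites that vary more on one procedure, and the protocol does not allow its direction to be predicted. The loss of power follows from any exclusion of a whole site, whatever the reason for it.

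**What to change.** In Appendix B, part C, delete the words "consideration given to exclusion of data from that surgeon and/or site from final analyses" together with the joining 'and' before them. Keep the proficiency evaluation that the same sentence already requires. Add one sentence, there or in K.3: the primary analysis includes all randomised women from all sites and surgeons in their assigned arm, and any analysis without a surgeon or site is reported as a labelled sensitivity analysis.

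The cost is two short edits and no new data. The design figures (260 evaluable per group, 80.0% power) then stand as planned. The downside is that a poorly performing surgeon or site stays in the primary estimate; the sensitivity analysis shows how much it matters.
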